## **10. STUDY GOVERNANCE CONSIDERATIONS**

### **10.1. Posting of Information on Publicly Available Clinical Trial Registers**

Study information from this protocol will be posted on publicly available clinical trial registers before enrolment of subjects begins.

### **10.2. Regulatory and Ethical Considerations, Including the Informed Consent Process**

Prior to initiation of a study site, GSK will obtain favourable opinion/approval from the appropriate regulatory agency to conduct the study in accordance with ICH Good Clinical Practice (GCP) and applicable country-specific regulatory requirements.

The study will be conducted in accordance with all applicable regulatory requirements.

The study will also be conducted in accordance with ICH Good Clinical Practice (GCP), all applicable subject privacy requirements, and, the guiding principles of the **1996 Declaration of Helsinki**. This includes, but is not limited to, the following:

- IRB/IEC review and favourable opinion/approval to conduct the study and of any subsequent relevant amended documents
- Written informed consent (and any amendments) to be obtained for each subject before participation in the study
- Investigator reporting requirements (e.g. reporting of AEs/SAEs/protocol deviations to IRB/IEC)

Written informed consent must be obtained from each subject prior to participation in the study.

#### **10.2.1. Urgent Safety Measures**

If an event occurs that is related to the conduct of the study or the development of the study treatment, and this new event is likely to affect the safety of subjects, the sponsor and the investigator will take appropriate urgent safety measures to protect subjects against any immediate hazard.

The sponsor will work with the investigator to ensure the IEC/IRB is notified.

### **10.3. Quality Control (Study Monitoring)**

In accordance with applicable regulations including GCP, and GSK procedures, GSK monitors will contact the site prior to the start of the study to review with the site staff the protocol, study requirements, and their responsibilities to satisfy regulatory, ethical, and GSK requirements. When reviewing data collection procedures, the discussion will also include identification, agreement and documentation of data items for which CRF will serve as the source document.

GSK will monitor the study and site activity to verify that the:

- Data are authentic, accurate, and complete.
- Safety and rights of subjects are being protected.
- Study is conducted in accordance with the currently approved protocol and any other study agreements, GCP, and all applicable regulatory requirements.

The investigator and the head of the medical institution (where applicable) agrees to allow the monitor direct access to all relevant documents

#### **10.4. Quality Assurance**

To ensure compliance with GCP and all applicable regulatory requirements, GSK may conduct a quality assurance assessment and/or audit of the site records, and the regulatory agencies may conduct a regulatory inspection at any time during or after completion of the study. In the event of an assessment, audit or inspection, the investigator (and institution) must agree to grant the advisor(s), auditor(s) and inspector(s) direct access to all relevant documents and to allocate their time and the time of their staff to discuss the conduct of the study, any findings/relevant issues and to implement any corrective and/or preventative actions to address any findings/issues identified.

#### **10.5. Study and Site Closure**

Upon completion or premature discontinuation of the study, the monitor will conduct site closure activities with the investigator or site staff, as appropriate, in accordance with applicable regulations including GCP, and GSK procedures.

In addition, GSK reserves the right to temporarily suspend or prematurely discontinue this study at any time for reasons including, but not limited to, safety or ethical issues or severe non-compliance. For multicenter studies, this can occur at one or more or at all sites. If GSK determines such action is needed, GSK will discuss this with the investigator or the head of the medical institution (where applicable), including the reasons for taking such action. When feasible, GSK will provide advance notification to the investigator or the head of the medical institution, where applicable, of the impending action prior to it taking effect.

If the study is suspended or prematurely discontinued for safety reasons, GSK will promptly inform investigators or the head of the medical institution (where applicable) and the regulatory authorities of the suspension or premature discontinuation of the study and the reason(s) for the action. If required by applicable regulations, the investigator or the head of the medical institution (where applicable) must inform the IRB/IEC promptly and provide the reason for the suspension or premature discontinuation.

#### **10.6. Records Retention**

Following closure of the study, the investigator or the head of the medical institution (where applicable) must maintain all site study records, except for those required by local regulations to be maintained by someone else, in a safe and secure location. The records

must be maintained to allow easy and timely retrieval, when needed (e.g., audit or inspection), and, whenever feasible, to allow any subsequent review of data in conjunction with assessment of the facility, supporting systems, and staff. Where permitted by local laws/regulations or institutional policy, some or all of these records can be maintained in a format other than hard copy (e.g., microfiche, scanned, electronic); however, caution needs to be exercised before such action is taken. The investigator must assure that all reproductions are legible and are a true and accurate copy of the originals, and meet accessibility and retrieval standards, including re-generating a hard copy, if required. Furthermore, the investigator must ensure there is an acceptable back-up of these reproductions and that an acceptable quality control process exists for making these reproductions.

GSK will inform the investigator of the time period for retaining these records to comply with all applicable regulatory requirements. The minimum retention time will meet the strictest standard applicable to that site for the study, as dictated by any institutional requirements or local laws or regulations, or GSK standards/procedures; otherwise, the retention period will default to 15 years.

The investigator must notify GSK of any changes in the archival arrangements, including, but not limited to, archival at an off-site facility or transfer of ownership of the records in the event the investigator leaves the site.

#### **10.7. Provision of Study Results to Investigators, Posting of Information on Publically Available Clinical Trials Registers and Publication**

Where required by applicable regulatory requirements, an investigator signatory will be identified for the approval of the clinical study report. The investigator will be provided reasonable access to statistical tables, figures, and relevant reports and will have the opportunity to review the complete study results at a GSK site or other mutually-agreeable location.

GSK will also provide the investigator with the full summary of the study results. The investigator is encouraged to share the summary results with the study subjects, as appropriate.

GSK will provide the investigator with the randomization codes for their site only after completion of the full statistical analysis.

The results summary will be posted to the Clinical Study Register no later than eight months after the final primary completion date, the date that the final subject was examined or received an intervention for the purposes of final collection of data for the primary outcome. In addition, a manuscript will be submitted to a peer reviewed journal for publication no later than 18 months after the last subject's last visit (LSLV). When manuscript publication in a peer reviewed journal is not feasible, a statement will be added to the register to explain the reason for not publishing.

## 12. APPENDICES

### 12.1. Appendix 1: Liver Safety Process

The procedures listed below are to be followed if a subject meets the liver chemistry stopping criteria defined in Section 5.7.1:

- Immediately withdraw the subject from study treatment
- Notify the GSK medical monitor within 24 hours of learning of the abnormality to confirm the subject's study treatment cessation and follow-up.
- Complete the "Safety Follow-Up Procedures" listed below.
- Complete the liver event case report forms. If the event also meets the criteria of an SAE (see Section 7.1.4), the SAE data collection tool will be completed separately with the relevant details.
- Upon completion of the safety follow-up withdraw the subject from the study unless further safety follow up is required
- Do not restart investigational product
- Refer to the Flow chart for a visual presentation of the procedures listed below.

#### **Safety Follow-Up Procedures for subjects with $ALT \geq 3 \times ULN$ :**

- Monitor subjects weekly until liver chemistries (ALT, AST, alkaline phosphatase, bilirubin) resolve, stabilize or return to within baseline values.

#### **Safety Follow-Up Procedures for subjects with $ALT \geq 3 \times ULN$ and total bilirubin $\geq 2 \times ULN$ ( $> 35\%$ direct bilirubin); or $ALT \geq 3 \times ULN$ and $INR^1 > 1.5$ :**

- This event is considered an SAE (see Section 7.1.4). Serum bilirubin fractionation should be performed if testing is available. If fractionation is unavailable, urinary bilirubin is to be measured via dipstick (a measurement of direct bilirubin, which would suggest liver injury).
- Make every reasonable attempt to have subjects return to the clinic within 24 hours for repeat liver chemistries, additional testing, and close monitoring (with specialist or hepatology consultation recommended).
- Monitor subjects twice weekly until liver chemistries (ALT, AST, alkaline phosphatase, bilirubin) resolve, stabilize or return to within baseline values.

#### **In addition, for all subjects with $ALT \geq 3 \times ULN$ , every attempt must be made to also obtain the following:**

- Viral hepatitis serology including:

---

[figure not shown]
 INR testing not required per protocol and the threshold value does not apply to subjects receiving anticoagulants.

- Hepatitis A IgM antibody.
- Hepatitis B surface antigen and Hepatitis B Core Antibody (IgM).
- Hepatitis C RNA.
- Cytomegalovirus IgM antibody.
- Epstein-Barr viral capsid antigen IgM antibody (or if unavailable, obtain heterophile antibody or monospot testing).
- Hepatitis E IgM antibody.
- Blood sample for pharmacokinetic (PK) analysis, obtained within 24 hours of last dose. Record the date/time of the PK blood sample draw and the date/time of the last dose of study treatment prior to blood sample draw on the CRF. If the date or time of the last dose is unclear, provide the subject's best approximation. If the date/time of the last dose cannot be approximated OR a PK sample cannot be collected in the time period indicated above, **do not obtain a PK sample**. Instructions for sample handling and shipping are included in the SPM.
- Serum creatine phosphokinase (CPK) and lactate dehydrogenase (LDH).
- Fractionate bilirubin, if total bilirubin  $\geq$  2xULN.
- Assess eosinophilia
- Record the appearance or worsening of clinical symptoms of hepatitis (fatigue, nausea, vomiting, right upper quadrant pain or tenderness, fever, rash or eosinophilia) on the AE CRF.
- Record use of concomitant medications, acetaminophen, herbal remedies, other over the counter medications, or putative hepatotoxins on the Concomitant Medications CRF.
- Record alcohol use on the Liver Events CRF.

The following are required for subjects with ALT  $\geq$  3xULN **and** bilirubin  $\geq$  2xULN ( $>35\%$  direct) but are optional for other abnormal liver chemistries:

- Anti-nuclear antibody, anti-smooth muscle antibody, and Type 1 anti-liver kidney microsomal antibodies.
- Serum acetaminophen adduct HPLC assay (quantifies potential acetaminophen contribution to liver injury in subjects with definite or likely acetaminophen use in the preceding
- Liver imaging (ultrasound, magnetic resonance, or computerized tomography) to evaluate liver disease.
- The Liver Imaging and/or Liver Biopsy CRFs are also to be completed if these tests are performed.

Refer to the diagram below for a visual presentation of the procedures listed above.

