### **3.2.2.3. Additional preliminary data from Part B**

A population pharmacokinetic model integrating all plasma data from part A and the preliminary data from n=4 in part B lead to an estimation of the half life of 57 hours for GSK2646264. This model shows that in order to maintain a 1.8 fold margin with the  $AUC$  NOAEL to allow women of child bearing potential in the trial the doses of 180mg (10% BSA) should be administered every three days, over a total 7 day duration, rather than every day.

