## **5.6. Safety Related Study Specific Dose Adjustment Criteria**

If AEs which are of severe intensity and are similar across subjects in the group, or if unacceptable pharmacological effects, reasonably attributable in the opinion of the investigator to dosing with GSK2646264, or if dose limiting toxicity (see Section 5.5.1), are observed in 2 or more subjects in dosing group 1 or dosing group 2 of part A, the dose escalation will be stopped. Relevant reporting and discussion with the GSK medical monitor and the SMC will take place. A substantial amendment will be submitted to the Ethics committees and Regulatory authorities for approval prior to any resumption of dosing.

If AEs which are of severe intensity and are similar across subjects in either Part B or C, or if unacceptable pharmacological effects, reasonably attributable in the opinion of the investigator to dosing with GSK2646264, or if dose limiting toxicity (see Section 5.5.1), are observed in 2 or more subjects in either Part B or C, relevant reporting and discussion with the GSK medical monitor and the SMC will take place.

If a Serious Adverse Event (SAE) occurs in 1 subject and is deemed to be drug related, the dose escalation in Part A, or the study if in Part B or Part C, will be stopped. Relevant reporting and discussion with the GSK medical monitor and the SMC will take place. A substantial amendment will be submitted to the Ethics committees and Regulatory authorities for approval prior to any resumption of dosing.

The above criteria will apply regardless of whether pharmacokinetics are less than the above mentioned PK stopping criteria and every effort will be made to take a blood sample at the time of the event for pharmacokinetics analysis in the presence of any of the above events.

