## **5.7. Stopping Criteria for a subject**

### **5.7.1. Liver Chemistry Stopping Criteria**

Liver chemistry threshold stopping criteria have been designed to assure subject safety and to evaluate liver event aetiology (in alignment with the FDA premarketing clinical liver safety guidance).

Study treatment will be stopped **for a subject** if the following liver chemistry stopping criteria is met:

- ALT  $\geq$  3xULN

NOTE: Refer to [Appendix 1](#) for details of the required assessments if a subject meets the above criteria.

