### 5.7.3. Safety related Stopping criteria for an individual subject

A subject may be withdrawn from the study if they present dose limiting toxicity (as defined in Section 5.5.1; also refer to tolerability assessment definition in Section 6.3.4.1.). If dose limiting toxicity is observed in an individual, the Investigator or designee may use their medical judgment and stop dosing the individual subject, and is required to immediately inform the GSK medical monitor or designee. They will then decide whether it is necessary for the SMC to be convened immediately or not, for review of the data and decision on dose adjustment or withdrawal of the individual subject.

A subject may be withdrawn from the study if they present a Serious Adverse Event (SAE), regardless of its severity, and reasonably attributable in the opinion of the investigator to dosing with GSK2646264.

A subject will be withdrawn if they require concomitant medications listed in Section 5.15.

Dosing to an individual may be stopped due to unacceptable local tolerability as evidenced by dose limiting toxicity (as defined in Section 5.5.1).

Tolerability assessments on treated skin areas will be made using the criteria in Section 6.3.4.1.

In the presence of any of the above events, every effort will be made to take a blood sample at the time of the event for pharmacokinetics analysis.

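### Appendix 1 bars the event-triggered PK sample for a liver event more than 24 h after the last dose, which conflicts with Sections 5.6 and 5.7.3 for drug-related liver SAEs and does not fit a 57 h half-life

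*Protocol*

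**What the plan says.** Section 5.7.1 of the protocol sets the liver stopping threshold at ALT ≥3×ULN and gives a twofold purpose: "Liver chemistry threshold stopping criteria have been designed to assure subject safety and to evaluate liver event aetiology". It has no PK rule of its own and refers to Appendix 1.

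Appendix 1 lists tests that the site must try to obtain for all such subjects. One is: "Blood sample for pharmacokinetic (PK) analysis, obtained within 24 hours of last dose". It adds, in bold, that no PK sample is to be taken if the last-dose time cannot be approximated or if "a PK sample cannot be collected in the time period indicated above". This is a prohibition, not a preferred window.

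Section 5.6, after its list of study-level events, says that "every effort will be made to take a blood sample at the time of the event for pharmacokinetics analysis". Section 5.7.3, after its list of subject-level events, says: "In the presence of any of the above events, every effort will be made to take a blood sample at the time of the event". Neither sets a time limit.

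Section 7.1.4 and Appendix 1 class ALT ≥3×ULN with bilirubin ≥2×ULN (>35% direct), or with INR >1.5, as an SAE.

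On elimination, Section 3.2.2.3 reports that population modelling of Part A and the first four Part B subjects "lead to an estimation of the half life of 57 hours". Part C doses on Days 1, 4 and 7 (Section 3.1.5). Part B doses once daily for three days (Section 3.1.4).

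**The concern.** A sampling window is usually closed when a late sample would say little about exposure. Here it closes while most of the drug is still in the plasma. Appendix 6 predicted a half-life of 0.7 h, against which 24 h is ample. Other parts of the protocol fit the longer estimate: PK sampling runs to Day 17-19 in Part B and Day 22 in Part C, and contraception to at least 12 days after the last dose. Appendix 1 does not.

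The two sets of instructions also overlap. A liver SAE judged drug-related is covered by Appendix 1 and by Sections 5.6 and 5.7.3, and more than 24 h after dosing they say opposite things.

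At stake is the ability to relate a liver event to drug concentration in a first-in-human study where exposure ran above prediction. For 1% cream on 10% BSA, Appendix 5 predicted a Cmax of 1.29 ng/mL and an AUC of 30.71 ng·h/mL. Section 3.2.2.2 reports geometric means of 5.59 and 103.8 after four days of dosing (up to 10% BSA). The ratios are 5.59/1.29 = 4.3 and 103.8/30.71 = 3.4. The prediction covers 24 h, so accumulation explains part of the difference.

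**Working it through.** **1. The half-life.** The 57 h estimate cannot be recomputed, because its data are not in the documents. It is consistent with the 12-day contraception period: 5 × 57 h = 285 h = 11.9 days. The 0.7 h prediction does reproduce from clearance 13 mL/min/kg and volume 0.8 L/kg: ln 2 × 800 / 13 = 42.7 min = 0.71 h. The 24 h limit is therefore 24/0.71 ≈ 34 predicted half-lives, but only 24/57 = 0.42 of the current one.

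**2. What remains when sampling is barred.** First-order decay from the post-dose level, fraction = 2^(−t/57):

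| Time after dose | Remaining |
|---|---|
| 24 h | 74.7% |
| 48 h | 55.8% |
| 72 h | 41.7% |
| 192 h (Part C Day 15) | 9.7% |
| 360 h (Part C Day 22) | 1.3% |

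**3. How much time lies outside the window.** Share of time more than 24 h after the latest dose, from the dosing days and follow-up windows:

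- Part C, within a dosing interval: 48/72 = 66.7%. Days 1-8: 96/168 = 57%. To follow-up (Day 21-23): 408/480 to 456/528 = 85-86%.
- Part B, to Day 17-19: 312/384 to 360/432 = 81-83%.
- Part A group 1, to Day 5-7: 24/96 to 72/144 = 25-50%.
- Part A group 2, to Day 9-11: 96/192 to 144/240 = 50-60%.

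These are shares of time. They become shares of liver events only if events are spread evenly over time, which is an assumption.

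**4. Which events meet both instructions.**

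| Event | In the 5.6 or 5.7.3 list? | More than 24 h after the last dose |
|---|---|---|
| ALT ≥3×ULN alone | No (5.7.1 only) | No contradiction, but the bar applies |
| ALT ≥3×ULN with raised bilirubin or INR, judged drug-related | Yes | Opposite instructions |
| Similar severe, attributable liver AEs in 2 or more subjects | Yes (5.6) | Opposite instructions |
| Dose-limiting toxicity | Yes | Does not arise: onset is by definition within 6 h (Parts A, B) or 24 h (Part C) of a dose (5.5.1) |

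**5. What scheduled sampling covers.** In Part C (Section 6.1.4), post-dose liver chemistry is on Days 7 and 22. PK is on Days 1, 4, 7, 10, 15 and 22, so both chemistry days have PK. In Part B (Section 6.1.3), post-dose chemistry is on Day 3 and at follow-up. PK is on Days 1-4, 6, 9, 12, 15 and at follow-up, so again both have PK. The longest nominal gap between scheduled PK days is 7 days in Part C (Day 15 to 22) and 3-4 days in Part B.

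**The case against.** The strongest reply is that little is lost. Appendix 1 restricts only an additional sample. An ALT rise found at a scheduled post-dose draw in Part B or C has a scheduled PK sample on the same day. Section 6.4.3.1 allows PK samples at additional time points, and Section 6 lets time points be added by Note to File. Part B subjects are in-house until the Day 4 assessments and have PK through 24 h after the last dose. In Part C, if the Day 7 dose is given before that day's chemistry result is known, the last-dose clock restarts. No laboratory turnaround time is given, so how often a recall visit falls after 24 h cannot be stated.

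Most of this stands, and it rules out a stronger reading that a reader might infer: that the rule discards exposure data for most liver events. That would need an assumed event timing, would not be shown for Part A, and ignores the scheduled samples. It would also be wrong to infer that every ALT ≥3×ULN event meets contradictory instructions, or that the 72 h dosing interval applies beyond Part C.

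The reply does not remove the core. Scheduled samples do not cover a symptomatic event or a recall visit between PK days. A general permission to add samples does not cancel a specific, bolded instruction not to take one. The conflict for drug-related liver SAEs remains.

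**Conclusion.** The point holds within limits. Appendix 1 contradicts Sections 5.6 and 5.7.3 for liver events that are drug-related SAEs, or are otherwise listed there, once 24 h have passed since the last dose. For all ALT ≥3×ULN events, the 24 h limit does not fit the protocol's own half-life: about 75% of the concentration remains when triggered sampling is barred and, in Part C, 42% remains at the end of a 72 h interval. The loss is confined to the event-triggered sample, for events and recall visits between scheduled PK days.

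This rests on the 57 h estimate, on simple first-order decay, and on subjects taken off treatment still attending scheduled PK visits, which the protocol does not spell out. Part A data had already been reviewed under the current amendment, so the practical effect is in Parts B and C. No trial estimate changes. The gain is in safety attribution, and the correction is cheap enough to make.

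**What to change.** Reconcile Appendix 1 with Sections 5.6 and 5.7.3. Delete the 24 h limit and the instruction against taking a late sample. Ask instead for a PK sample as soon as possible after the liver event is identified, with sample time and last-dose time recorded. Section 5.12 already has site staff record dose times, so a late sample can be interpreted.

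Do not replace the limit with a cap of about five half-lives (12 days). Part C Day 22 is 15 days after the last dose and Part B follow-up is 14-16 days after it, so a liver event found at either visit would fall outside such a cap. Sections 5.6 and 5.7.3 also set no limit.

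The cost is a short edit to Appendix 1 and one extra blood tube at a liver follow-up visit that is already required. Some late samples may be near or below quantification; by Day 22 in Part C only about 1.3% of the post-dose level would remain.
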